### **5.2.4 Dose-Limiting Toxicities (Immediately Reportable to the Sponsor)**

During the DLT assessment window, adverse events identified as DLTs, as defined in Section 3.1.2.1.1, are required to be reported by the investigator to the Sponsor immediately (i.e., no more than 24 hours after learning of the event; see Section 5.4.2 for reporting instructions).

### **5.2.5 Selected Adverse Events**

Selected adverse events in this study are defined as adverse events for which additional data collection or analyses will be performed. Selected adverse events do not require immediate reporting if they are not serious (except for TLS).

The following adverse events are considered selected adverse events:

- Thrombocytopenia, including acute thrombocytopenia (events occurring during and within 24 hours following obinutuzumab infusion)
- Hepatitis B reactivation
- Cardiac events
- TLS
- IRRs
- All infections, including PML

- Neutropenia, including prolonged neutropenia (neutropenia < 1000 cells/μL that does not resolve after 28 days without obinutuzumab treatment) and late-onset neutropenia (neutropenia < 1000 cells/μL occurring ≥ 28 days after obinutuzumab treatment has been completed or stopped)
- Peripheral neuropathy (motor and/or sensory)
- Gastrointestinal perforation

Events for which additional data collection will be required are PML *and* hepatitis B reactivation.

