### **5.1.1.3 Neutropenia**

Grade 3 or 4 neutropenia, including febrile neutropenia, has been reported with obinutuzumab administration. Neutropenia resolved spontaneously or with use of hematopoietic growth factors. Patients who experience Grade 3 or 4 neutropenia should be closely monitored until neutrophil values return to at least Grade 2. Cases of late-onset neutropenia (ANC < 1000 cells/ $\mu$ L occurring  $\geq$  28 days after obinutuzumab treatment has been completed or stopped) or prolonged neutropenia (ANC < 1000 cells/ $\mu$ L that does not resolve after 28 days without obinutuzumab treatment) have also been reported. The use of G-CSF is allowed for treatment of neutropenia in this study. Prophylactic treatment with antibiotics should be administered as per standard practice. Guidelines for primary prophylaxis with G-CSF are provided in Section 4.4.1.

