### **5.1.2.5 Neutropenia (Including Prolonged Neutropenia)**

*Neutropenia is very common in patients receiving rituximab (occurring in  $\geq 10\%$  of patients) based on clinical trial experience. However, delayed onset neutropenia is very rare (occurring in  $< 1$  of 10,000 patients), and the incidence of prolonged neutropenia is unknown. Neutropenia may lead to serious or overwhelming infection, especially if profound (Grades 3–4), prolonged, associated with breaches in natural mucosal barriers (e.g., diarrhea and/or mucositis), and/or other immunological defects (e.g., lymphopenia, hypogammaglobulinemia, and acquired immunodeficiency syndrome). Despite an increase in incidence of neutropenia and Grade 3–4 neutropenia associated with rituximab, most studies have not reported a significant increase in serious neutropenic infections.*

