## 6.5 SAFETY ANALYSES

The safety analyses will include all treated patients (i.e., patients who received any amount of study treatment). Data for patients in the dose-escalation phase will be summarized by cohort *and histology type*, and data for patients in the expansion phase will be summarized by histologic subtype (FL or DLBCL).

Safety will be assessed through summaries of adverse events and changes from baseline in laboratory test results, shift-tables of ECGs findings, and vital signs.

All adverse events occurring on or after first study treatment will be summarized by mapped term, appropriate thesaurus levels, and NCI CTCAE, Version 4.0 grade. All serious adverse events, adverse events of special interest, and selected adverse events will be summarized and listed.

Deaths reported during the treatment period and during post-treatment follow-up will be listed *and summarized*.

Relevant laboratory *results* will be displayed by time, with Grade 3 and 4 values identified as appropriate.

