## Appendix 1 Schedule of Assessments for Patients with Follicular Lymphoma

	Screening a		Induction (6 months; 28-day cycles)								EOI	Maintenance (24 months)		EOM b	Post- Treatment FU Period (Q3M) d	Surviva l FU Period (Q3M) d
	D -28 to D -1	D -14 to D -1	Cycle 1 (±1 day)				Cycles 2-6 (±2 days)				After Last Induction Dose c	Monthly (±3 days)	Every 2 months (±1 wk)	35 Days after Last Dose		
			D1	D8	D15	D22	D1	D8	D15	D22		D1	D1			
Informed consent e	x															
Demographic data	x															
Medical history	x															
ECOG Performance Status	x															
Vital signs f	x		x	x	x		x					x		x		
Height	x															
Weight	x		x				x									
12-lead ECG	x										x g			x		
Complete physical examination h,i	x															
Targeted physical examination ij							D1, Cycles 2 and 4				x		x	x	x	
Ann Arbor, FLIPI, and FLIPI2	x															
B symptoms	x															
β 2 microglobulin			x m													
Hematology k		x	x l,m	x m	x m	x m	x m	x m,n	x m,n	x m,n	x g	x m		x		
Chemistry panel (serum or plasma) o		x	x l,m	x m	x m		x m		x m,n		x g	x m		x		
TSH, T3, T4	x		Every 3 months													

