## Appendix 2 Schedule of Assessments for Patients with Diffuse Large B-Cell Lymphoma

	Screening a		Induction (6 months; 28-day cycles)								EOI	Consolidation (6 months)		EOC b	Post- Treatment FU Period (Q3M) d	Survival FU Period (Q3M) d
	D -28 to D -1	D -14 to D -1	Cycle 1 (±1 day)				Cycles 2-6 (±2 days)				After Last Induction Dose c	Monthly (±3 days)	Every 2 months (±1 wk)	35 Days after Last Dose		
			D1	D8	D15	D22	D1	D8	D15	D22						
Informed consent e	x															
Demographic data	x															
Medical history	x															
ECOG Performance Status	x															
Vital signs f	x		x				x					x		x		
Height	x															
Weight	x		x				x									
12-lead ECG	x										x g			x		
Complete physical examination h,i	x															
Targeted physical examination ij							D1, Cycles 2 and 4				x		x	x	x	
Ann Arbor and IPI	x															
B symptoms	x															
β 2 microglobulin			x													
Hematology k		x	x l,m	x m	x m	x m	x m	x m,n	x m,n	x m,n	x g	x m		x	x	
Chemistry panel (serum or plasma) o		x	x l,m		x m		x m		x m,n		x g	x m		x	x	
TSH, T3, T4	x		Every 3 months													

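### Prolonged and late-onset neutropenia are defined for obinutuzumab only, while scheduled blood counts continue into post-treatment follow-up only in the rituximab (DLBCL) group

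*Combined protocol and SAP*

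**What the plan says.** Section 5.2.5 introduces the category: "Selected adverse events in this study are defined as adverse events for which additional data collection or analyses will be performed". Neutropenia is on the list, with two named subtypes. Prolonged neutropenia is a count below 1000 cells/μL still unresolved after 28 days off obinutuzumab. Late-onset neutropenia is a count below 1000 cells/μL at least "28 days after obinutuzumab treatment has been completed or stopped". Rituximab appears in neither definition. Section 6.5 commits to an analysis: "All serious adverse events, adverse events of special interest, and selected adverse events will be summarized and listed".

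The risk sections give the background. Section 5.1.1.3 (obinutuzumab) says that "Cases of late-onset neutropenia" have been reported, as have prolonged cases. Section 5.1.2 lists prolonged neutropenia among the rituximab risks, and 5.1.2.5 adds that "the incidence of prolonged neutropenia is unknown", while "delayed onset neutropenia is very rare" (fewer than 1 in 10,000 patients).

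The two schedules differ. In Appendix 1 (FL), hematology is marked through induction, at EOI only for patients not going on to maintenance (footnote g), monthly in maintenance, and at EOM, "35 Days after Last Dose". The post-treatment follow-up cell is blank. In Appendix 2, "Schedule of Assessments for Patients with Diffuse Large B-Cell Lymphoma", the same row is marked at end of consolidation (EOC) and again in the 3-monthly post-treatment follow-up column.

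**The concern.** The group to which the definitions apply has no scheduled count beyond EOM or EOI. The group with follow-up counts has no definition for the two subtypes. Late-onset neutropenia has a lower time limit of 28 days and no upper limit, so most of the period it describes is unobserved by schedule in FL. Its frequency there would tend to be under-counted, and it could not be set beside the DLBCL figure on a common basis.

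Section 5.1.5 anticipates overlapping hematologic toxicity, neutropenia in particular, so this bears on a main safety question of the study. Version 2 of the protocol moved DLBCL patients from obinutuzumab to rituximab and edited 5.2.5 for second malignancies, but left the neutropenia wording unchanged. No reason is given for counting in DLBCL follow-up and not in FL follow-up, so an oversight is a reasonable inference, though only an inference.

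**Working it through.** The plan states no figure to reproduce. The check compares visit days with the definition and the reporting window.

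**Inputs**
- Late-onset threshold: day 28 or later after obinutuzumab ends, count < 1000 cells/μL (5.2.5).
- A month is 28 days. The last maintenance obinutuzumab dose is Month 23 Day 1, and lenalidomide stops after at most 12 months (Table 5). For a completer, obinutuzumab is therefore the last study drug.
- EOM is 35 days after the last dose. EOI is 6–8 weeks after Day 1 of the last induction cycle (Appendix 1, footnote c).
- Adverse events are reported until 90 days after the last dose of study treatment (5.3.1).
- The first follow-up visit is 3 months after the last dose with maintenance, or 3 months after EOI without it (Appendix 1, footnote d).
- Enrollment: FL 18–30 in escalation plus 40 in expansion; DLBCL 12–18 plus 40 (6.1).

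**The two hematology rows.** Both have 16 visit cells. They differ in one: post-treatment follow-up is blank in FL and marked in DLBCL. The chemistry rows show the same difference in that column. The FL targeted-examination row is marked there, so the visit itself exists. No Appendix 1 footnote restores a neutrophil count: footnote m covers induction and maintenance, and the immunophenotyping panel (footnote v) covers only B, T and NK cells.

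**FL patient completing maintenance, days from the last obinutuzumab dose**
- Month 24 Day 1 is day 28. The count may be drawn up to 72 hours earlier (footnote m), so nominally on days 25–28, at the edge of the definition.
- EOM is day 35, which is 35 − 28 = 7 days into the late-onset period.
- Remaining adverse event period without a scheduled count: 90 − 35 = 55 days, and nothing later.
- First follow-up visit: 3 × 28 = day 84, or about day 91 in calendar months. No count is scheduled.

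**FL patient without maintenance, days from Day 1 of the last induction cycle**
- EOI is at days 6 × 7 = 42 to 8 × 7 = 56. This is the one count at or after day 28. For early discontinuation because of an adverse event, EOI may be 4–8 weeks (28–56 days) after the last dose of study treatment.
- First follow-up visit: 42 + 84 = 126 to 56 + 91 = 147.
- If Cycle 6 is completed, the last lenalidomide dose (Day 21) falls 20 days after Day 1, so adverse event reporting ends at 20 + 90 = day 110. The follow-up visit comes after that.

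**Numbers concerned.** FL: 18 + 40 = 58 to 30 + 40 = 70. DLBCL: 12 + 40 = 52 to 18 + 40 = 58.

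**The case against.** A good deal can be said on the other side.

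- **FL coverage is not nil.** A reader might infer that FL patients have no blood count in the late-onset period. The EOM count, or the EOI count, falls at or after day 28, so the documents do not support that. The gap begins after that count.
- **DLBCL events are not lost.** A reader might infer that low counts in DLBCL have no place in the selected adverse event summary. The listed item is neutropenia as a whole, so a reported event enters the 6.5 summary by grade. Only the subtype label is missing.
- **Delayed onset with rituximab is stated to be very rare.** At fewer than 1 in 10,000, 58 patients give fewer than 58 / 10,000 = 0.006 expected events. This stands. The case for a rituximab definition rests mainly on prolonged neutropenia.
- **Known cases are followed.** Section 5.1.1.3 asks for close monitoring of Grade 3 or 4 neutropenia, and 5.5.1 requires each adverse event to be followed to resolution or stability. This largely covers prolonged neutropenia once found, as do monthly counts in maintenance. It does not detect new late-onset cases.
- **FL infections of Grade 3 and 4 are collected for 2 years after obinutuzumab (5.3.1).** This captures an important consequence, but without a scheduled neutrophil count to help interpret it.
- **Follow-up counts fall mostly outside the 90-day period.** A reader might expect 3-monthly counts to correct the adverse event summary. They would add mainly laboratory data, because non-serious events are not reported after day 90. This stands and shapes the remedy.
- **Column alignment.** In the text form of Appendix 1, the immunoglobulin and immunophenotyping rows carry a 3-monthly follow-up footnote (s) under EOM, which suggests a shift in those rows. The hematology row shows no such sign, but the laid-out table should be checked.

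**Conclusion.** The inconsistency is real and modest in size. Section 5.2.5 and the two schedules do not match: FL has the subtype definitions but no scheduled hematology after EOM or EOI, and DLBCL has follow-up hematology but no subtype definitions that can be applied. Late-onset cases in FL after the last count will be found only by symptoms or unscheduled tests, so their incidence may be understated. In DLBCL, prolonged neutropenia, a listed risk of unknown incidence, cannot be summarized as such.

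The FL part is the stronger. The 58–70 FL patients are an upper bound, because those who progress move to survival follow-up, where neither appendix schedules hematology. The conclusion assumes that the hematology rows are aligned as they read and that no laboratory manual or other study document adds a count.

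A reader might also infer that the acute thrombocytopenia definition in 5.2.5 should be widened to rituximab. The documents do not support that: 5.1.2 does not list thrombocytopenia as a rituximab risk.

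**What to change.** 1. In Appendix 1, mark hematology in the post-treatment follow-up (every 3 months) column, as in Appendix 2, or state why the two groups differ.
2. In 5.2.5, define prolonged and late-onset neutropenia relative to the anti-CD20 antibody received (obinutuzumab or rituximab). Leave the acute thrombocytopenia definition as it is.
3. In 6.5, state that counts after the 90-day adverse event period are summarized by group from laboratory data, using the same threshold of < 1000 cells/μL. Section 6.5 already plans laboratory displays over time with Grade 3 and 4 values identified, so this is a small addition. Without it, the extra FL counts would have no planned analysis under these definitions.

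The cost is one routine local blood count at FL visits that already take place and include a physical examination, plus a few lines of text. The reported rate of late neutropenia may rise because more of it is observed.

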### **5.3 METHODS AND TIMING FOR CAPTURING AND ASSESSING SAFETY PARAMETERS**

The investigator is responsible for ensuring that all adverse events (see Section 5.2.1 for definition) are recorded on the Adverse Event eCRF and reported to the Sponsor in accordance with instructions provided in this section and in Sections 5.4–5.6.

For each adverse event recorded on the Adverse Event eCRF, the investigator will make an assessment of seriousness (see Section 5.2.2 for seriousness criteria), severity (see Section 5.3.3), and causality (see Section 5.3.4).

#### **5.3.1 Adverse Event Reporting Period**

Investigators will seek information on adverse events at each patient contact. All adverse events, whether reported by the patient or noted by study personnel, will be recorded in the patient’s medical record and on the Adverse Event eCRF.

**After informed consent has been obtained but prior to initiation of study treatment**, only serious adverse events caused by a protocol-mandated intervention (e.g., invasive procedures such as biopsies, discontinuation of medications) should be reported (see Section 5.4.2 for instructions for reporting serious adverse events).

**After initiation of study treatment**, all adverse events will be reported until 90 days after the last dose of study treatment. After this period, the investigator should report any serious adverse events that are believed to be related to prior study treatment *and events of second malignancies for patients who received obinutuzumab* (see Section 5.6).

An exception is *for the FL patients, where* Grade 3 and 4 infections (both related and unrelated) should be reported until up to 2 years after the last dose of *obinutuzumab*.

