- The classification of second malignancy has been changed from a selected adverse event to an adverse event of special interest in order to more closely monitor this adverse event. The duration of reporting has been extended (Sections 5.3.1 and 5.6).
- The adverse event reporting period for Grade 3 and 4 infections has been clarified: up to 2 years after last dose of study treatment only for patients receiving obinutuzumab (Section 5.3.1).
- Guidelines for the second and subsequent infusion of obinutuzumab have been clarified (i.e., patients with no infusion-related reaction during prior infusion will receive only an analgesic/antipyretic as premedication). Figure 6 and Table 13 have been updated accordingly.
- Thyroid hormone monitoring (thyroid-stimulating hormone, triiodothyronine, thyroxine) has been added at baseline and every 3 months (Section 4.5.6, Appendix 1, and Appendix 2).
- Recommendations on management of dermatologic toxicities has been updated to consider lenalidomide dose reduction or allow resuming current dose in the case of a Grade 2 or Grade 3 rash without blistering (Table 19).
- Reasons for permanent discontinuation of all drugs in the event of certain dermatologic toxicities have been updated to align with lenalidomide labeling recommendations (Table 19).
- Populations to be analyzed have been defined (Section 6.2).
- Interim analysis has been clarified, including specification that enrollment would not be stopped in the case of higher-than-expected efficacy (Section 6.10).

Clarifications to the protocol are summarized as follows:

- The safety objective has been clarified: RP2D will not be determined for polatuzumab vedotin in patients with R/R DLBCL, as it will be a fixed dose (Section 2.1).

- The secondary efficacy objective has been clarified: Complete response (CR) at end of induction (EOI) on the basis of computed tomography (CT) alone is to be determined by the Independent Review Committee in addition to the investigator (Sections 2.2.2 and 6.6.2).
- The exploratory efficacy objective has been clarified: If a patient with DLBCL has a positive positron emission tomography (PET)-CT scan at EOI, then they should have PET-CT scan repeated at end of consolidation (Section 2.2.3, Section 6.6.3, and footnote "jj" in Appendix 2).
- The number of patients in the study has been updated (Sections 3.1.1, 3.1.2, and 6.1).

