## **3.2 END OF STUDY AND LENGTH OF STUDY**

The end of this study is defined as the time when both of the following criteria are met:

- All enrolled patients with FL have *been followed for at least 90 days after they have completed or discontinued study treatment (including induction treatment and maintenance treatment as applicable)*.
- All enrolled patients with DLBCL have been followed for at least 1 year after they have completed or discontinued study treatment (including induction treatment and consolidation treatment as applicable).

The total length of the study, from screening of the first patient to the end of the study, is expected to be approximately 5 years.

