### **5.1.2.2 Infections (Including Serious Infections)**

Serious infections, including fatal bacterial, fungal, and new or reactivated viral infections, can occur during and up to 1 year following completion of rituximab-based therapy.

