### **5.1.2.4 Progressive Multifocal Leukoencephalopathy**

Rare cases of PML have also been reported in patients treated with rituximab alone or in combination with other immunosuppressive medications (Goldberg et al. 2002; Calabrese et al. 2007; Carson and Bennett 2009). In a review of 57 patients who developed PML after rituximab administration, all patients had received prior therapies with alkylating agents, corticosteroids, purine analogs, or drugs to prevent allogeneic stem cell or solid-organ graft rejection. The diagnosis of PML in any patient treated with rituximab is rare, but it should be suspected in any patient who develops new-onset neurologic manifestations. The majority of patients with hematologic malignancies diagnosed with PML received rituximab in combination with chemotherapy or as part of a hematopoietic SCT. Most cases of PML were diagnosed within 12 months of the patients' last infusion of rituximab.

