## **5.6 ADVERSE EVENTS THAT OCCUR AFTER THE ADVERSE EVENT REPORTING PERIOD**

The Sponsor should be notified if the investigator becomes aware of any serious adverse event that occurs after the end of the adverse event reporting period (defined as 90 days after the last dose of study treatment), if the event is believed to be related to prior study treatment. *The sponsor should also be notified of events of second malignancies after the end of the adverse event reporting period for patients who received obinutuzumab.*

An exception is *for patients receiving obinutuzumab, where Grade 3–4 infections (both related and unrelated) should be reported until up to 2 years after the last dose of study treatment.*

The investigator should report these events directly to the Sponsor or its designee, either by faxing or by scanning and emailing the Serious Adverse Event/Adverse Event of Special Interest Reporting *Form* using the fax number or email address provided to investigators.

During survival follow-up, deaths attributed to progression of lymphoma should be recorded only on the Study Completion/Early Discontinuation eCRF.

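### In DLBCL, infections judged unrelated and non-serious Grade 3 infections are not reportable beyond 90 days, although the protocol puts the serious-infection risk after rituximab at up to 1 year

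*Combined protocol and SAP*

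**What the plan says.** **Reporting window.** Under Section 5.3.1, "all adverse events will be reported until 90 days after the last dose of study treatment". The rule then narrows: "After this period, the investigator should report any serious adverse events that are believed to be related to prior study treatment", with second malignancies added for patients who received obinutuzumab. Sections 5.4.2.2 and 5.6 carry the same limit for serious events.

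**Infection exception.** For FL patients, Section 5.3.1 adds that "Grade 3 and 4 infections (both related and unrelated) should be reported until up to 2 years after the last dose of" obinutuzumab. Section 5.6 gives the exception to patients receiving obinutuzumab, whose Grade 3–4 infections "should be reported until up to 2 years after the last dose of study treatment". Under the current protocol these are the same patients, because DLBCL patients receive rituximab, although the two sections start the 2 years from different doses. Footnote aa of Appendix 1 (FL) carries the exception. Footnote z of Appendix 2 (DLBCL) does not.

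**Stated risk.** Section 5.1.2.2 says serious infections, some fatal, "can occur during and up to 1 year following completion of rituximab-based therapy". Section 5.1.2.4 adds, for PML: "Most cases of PML were diagnosed within 12 months of the" last rituximab infusion. Section 5.2.5 lists all infections, including PML, as selected adverse events, with no restriction by histology.

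**Follow-up.** Section 3.2 ends the study only when "All enrolled patients with DLBCL have been followed for at least 1 year after they have completed or discontinued study treatment". Section 3.1.6 and Appendix 2 schedule 3-monthly assessments for progression-free patients, with hematology, chemistry and immunoglobulins. After progression there is a 3-monthly contact for survival and new treatment.

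**The concern.** The protocol names a hazard lasting up to a year after rituximab-based therapy and marks infections for additional data collection or analysis. It then stops unconditional reporting after 90 days in the cohort given rituximab. From that point a serious infection is reported only if the investigator believes it is related. In an open-label, single-arm study of a new triplet, that single causality judgment decides whether the event reaches the safety tables. An infection in a DLBCL patient can readily be put down to the lymphoma or to background immunosuppression.

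At stake is how completely late infections are described for R+Pola+Len. Sections 5.1.3.1 and 5.1.4.2 attach a neutropenia risk to polatuzumab vedotin and to lenalidomide as well. Late infection counts in FL and DLBCL would also rest on different ascertainment rules without the tables saying so.

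**Working it through.** The plan states no figure for this gap, so there is none to reproduce. The check is a comparison of rules followed by date arithmetic.

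**Step 1: what remains reportable in DLBCL after day 90** (Sections 5.3.1, 5.4.2.2 and 5.6; Appendix 2 footnote z)

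| Infection | Reportable? |
|---|---|
| Serious, judged related | Yes, no time limit |
| Serious, judged unrelated | No |
| Non-serious Grade 3, judged related | No |
| Non-serious Grade 3, judged unrelated | No |

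A late fatal infection judged unrelated would still appear as a death, since Section 6.5 lists and summarises deaths in post-treatment follow-up. The infection itself need not be recorded: Section 5.3.5.8 sends late deaths to Section 5.6, which covers related serious events and lymphoma deaths.

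**Step 2: inputs**
- Risk period: 1 year = 365 days (5.1.2.2).
- Reporting window: 90 days from the last dose of any study treatment (5.3.1).
- Consolidation: rituximab on Day 1 of Months 1, 3 and 5; lenalidomide on Days 1–21 of each month for up to 6 months; a month is 28 days (Table 10).
- Induction: rituximab on Day 1 and lenalidomide on Days 1–21 of each of six 28-day cycles (Table 9).

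**Step 3: both clocks from the end of rituximab-based therapy**

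Gap = 365 − 90 = 275 days; 275/365 = 75%, about 9.0 calendar months.

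**Step 4: risk year from the last rituximab infusion, 90 days still from the last dose of any drug**
- Consolidation completer: Month 5 Day 1 to Month 6 Day 21 is 28 + 20 = 48 days. Gap = 365 − 90 − 48 = 227 days; 227/365 = 62%, about 7.5 months.
- Stops after Cycle 6: Cycle 6 Day 1 to Day 21 is 20 days. Gap = 365 − 90 − 20 = 255 days; 255/365 = 70%, about 8.4 months.

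Both Step 4 cases assume dosing on schedule.

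**Step 5: does a one-year window fit the planned follow-up?** Section 3.2 follows DLBCL patients for at least 1 year from the end of study treatment. The last rituximab dose is 20 to 48 days earlier in the Step 4 cases, so a year counted from it ends inside the minimum follow-up.

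**The case against.** The strongest reply is that the difference is intended and drug-specific. The list of changes for Amendment 2 describes the infection rule as "up to 2 years after last dose of study treatment only for patients receiving obinutuzumab". There is support for treating the drugs differently: Section 5.1.1 lists prolonged B-cell depletion and late-onset neutropenia among identified obinutuzumab risks, while the rituximab list in Section 5.1.2 omits the former and Section 5.1.2.5 calls delayed-onset neutropenia very rare. Obinutuzumab maintenance also lasts up to 24 months, against 6 months of consolidation. This stands, and it means the absence of a 2-year window in DLBCL is not an oversight. It does not explain why the 1-year rituximab statement, added in the same amendment, has no matching reporting rule.

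A reader might infer that late infections in general, PML included, are lost in DLBCL. The documents do not support that. Related serious infections have no cut-off, Section 5.3.4 tells investigators to weigh known associations with treatment, and Section 5.2.5 requires extra data on PML. Most PML would probably still be captured, so it is a weak example.

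A reader might also take 75% as the share of late infections missed, or as the cohort's lost follow-up. It is neither. It is a maximum share of time for one patient. Treatment stops at progression, and the protocol's own figures suggest early progression: a median PFS of 5.6 months with rituximab plus polatuzumab vedotin at 2.4 mg/kg in DLBCL (Section 1.3.2.1), and about 7 months as the longest for the rituximab regimens discussed in Section 3.3.3.4. New therapy would often shorten the relevant period.

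Finally, safety is descriptive and summarised by histology. No formal FL-versus-DLBCL comparison or 1-year infection rate is planned, so no planned inference fails. That is correct and limits the weight of the point.

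**Conclusion.** The point holds within limits. In DLBCL, two kinds of infection are not reportable more than 90 days after the last dose: those judged unrelated, and non-serious Grade 3 infections whether or not judged related. The unreconciled sections are 5.1.2.2 on one side and 5.3.1, 5.6 and Appendix 2 footnote z on the other.

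For a patient alive and off new therapy, the uncovered part of the risk year is at most 275 days (75%) from the end of rituximab-based therapy, or 227 to 255 days (62–70%) from the last rituximab infusion. It is shorter once new therapy starts. The range assumes on-schedule dosing and takes the 1-year statement at face value.

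The documents give no rate of late unrelated infections, so neither the size nor the existence of a material undercount can be shown. What can be shown is that late ascertainment depends on seriousness and an open-label causality judgment in one histology and not in the other. It is worth correcting because the change is small.

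**What to change.** In Sections 5.3.1 and 5.6 and Appendix 2 footnote z, require Grade 3–5 infections in DLBCL, regardless of relatedness, to be reported until 1 year after the last rituximab dose or the start of new anti-lymphoma therapy, whichever is first. State how this relates to Section 5.1.2.2. If the year there is read as starting from the last dose of any component, the proposed window ends 20 to 48 days short of it in the two on-schedule cases, a small residue.

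Collect the events at the existing 3-monthly post-treatment visits; Section 5.3.1 already has investigators seek adverse events at each contact. Patients who have progressed but not started new therapy have no safety visit, so for them add the question to the existing 3-monthly survival contact. Footnote d of Appendix 2 defines the end of study without the follow-up year in Section 3.2 and should be aligned with it, since the window relies on that year.

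Report late DLBCL infections with their ascertainment window stated. A summary by patient-time at risk is optional.

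The cost is revised wording and some extra site data entry, with no added visits. Capture after progression will be less complete, and the report should say so. Only data collection changes; no dose or clinical rule is affected.
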